9.3.3 Outcome measures

All outcomes will be identified by using inpatient hospital data with either primary and or secondary discharge diagnoses.

[figure not shown]
The primary effectiveness outcome of this study is ischemic stroke and the primary safety outcome of this study is ICH.

Events are defined as hospitalizations with the respective ICD-10-GM diagnosis (see Table 6).

The secondary outcome will be occurrence of any one single event (as listed above).

Incidence rates, as well as adjusted and unadjusted hazard ratios will be estimated comparing the risk for a cardiovascular endpoint in patients initiating Rivaroxaban versus Phenprocoumon.

Figure 2. Study Period and Outcome Variables

9.4 Data sources

Health insurance in Germany

Approximately 86% of the German population, corresponding to about 70 million individuals, is insured in the statutory health insurance (SHI). Out of the remaining 14%, 11% of the German population is covered by the private health insurances and 3% are covered by special programs which include soldiers and policemen. The SHI is structured in ~120 different and independent health insurances. All individual health insurances offer the same comprehensive benefit package, as the contents to be reimbursed are set in Social Law. Nearly full coverage for all health care related services is provided as only little co-payments exist. Therefore, the funds paid by the SHI to any provider of health care (hospital, physician or pharmacist) represent almost the complete spectrum of total health care cost on an individual patient basis. All data can be linked to patients' demographics including age, gender, and the type of occupation for individuals within the workforce. However, health insurances in Germany do not have knowledge of any clinical data, such as clinical parameters (e.g. lab test results, results of bone density tests, quality of life data, severity grades of a disease, symptom scores etc.). A health insurance has a record for the test or procedure in every case as they have to pay for it but no record of the clinical finding as mentioned.

Description of the database

The HRI research database comprises claims data from about 75 different health insurances, which represents a high percentage of the overall number of health insurances in Germany. Data on patients and physicians is anonymized, as are the providers and the sickness funds, before data is made available to the HRI. The analysis sample of the HRI database includes the utilization and costs of services for approximately 4 million covered lives in 2013 on an anonymized case-by-case individual level. This sample represents 4.8% of the German population and 5.6% of the German SHI population. The insured individuals are distributed all over Germany. Furthermore, the sample is already structured to be representative for the German population in terms of age and gender (structure of age and gender as per 31.12.2013 / DESTATIS).

Almost 80% of the insured individuals in the database are observable for the entire available observation period of up to six years. Thus, analyses including comparatively large study populations with a long observation period are possible.

The HRI database is updated on an annual basis, guaranteeing studies with the most recent data. As the database has an administrative time lag until completion and clean up for all areas of health care of about 9 months, most data will be available for the preceding year, mid of the following calendar year.

Structure of the database

The database refers to different health care sectors such as the inpatient, outpatient, and pharmacy sector, and provides detailed information on the resource use and cost of these services. It includes amongst others, the following data:

- **Patient Demographics:** Record of continuous enrollment for a unique set of demographics (e.g. insurance begin and end, age, gender, date of death, which relates to the beginning of the quarter) for each individual. In addition, the insurance status (e.g. retired, family insurance), region of residence, and the type of occupation are included.
- **Inpatient Care:** Contains records that summarize hospital admission information such as ICD-10-GM (German Modification of the ICD-10 codes) codes in primary or secondary position, and Diagnosis Related Groups (DRG) code. It also includes the length of stay (date of hospital admission and end of hospital stay) and all performed procedures and surgeries (OPS). Furthermore, discharge diagnosis code or death in hospital, and costs of inpatient stay are included.
- **Outpatient Care:** Contains services that were rendered in a physician's office in the quarter in which the diagnosis (ICD-10-GM code) was documented. In addition, the procedures performed (e.g. laboratory, radiology echocardiography) by EBM codes and day of performance. Furthermore, the type of specialist that documented the diagnosis and performed the procedure (e.g. cardiologist, general practitioner) and costs of outpatient care are available.
- **Pharmaceutical Claims:** Contains drug dispensed by PZN (package level) – this is mapped to ATC codes and DDDs, day of prescription, day of dispensing, and costs of drugs dispensed from a statutory health insurance perspective without individual deductibles between single sickness funds and pharmaceutical companies. Furthermore, the type of doctor prescribing (e.g. cardiologist, general practitioner) is included.
- **Devices and Aids:** Contains type of device/aid (code and text) (e.g. massage, occupational therapy, walker, wheel chair), quantity prescribed, type of care provider, start and end date, and costs of device/aids.
- **Incapacity to Work and Sick Leave Payments:** This includes ICD-10-GM diagnoses that cause sick leave, duration of sick leave, and the corresponding start and end date of sick leave. In addition, the type of physician that filled-out the sick leave (e.g., cardiologist, general practitioner) and the cost of sick leave payments are incorporated.

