9.2.1 Study time frame

The evaluation time frame the study will be January 1, 2011 through March 31, 2016.

For both groups (Rivaroxaban and Phenprocoumon), the date of the first Rivaroxaban or Phenprocoumon dispensing will reflect the index date and mark the beginning of the observation period. Patient baseline characteristics will be measured during the 12 months (365 days, four quarters) preceding the index date (baseline period). The observation (follow-up) period will span from the index date up until the end of data, disenrollment, discontinuation of index treatment (30 day gap period allowed), occurrence of event or switch of treatment.

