We will perform 1:1 nearest-neighbor matching. After matching, we expect to see balance between the Rivaroxaban and VKA groups with respect to all measured factors. To ensure this, we will examine propensity score balance diagnostics including: (1) pre- and post-matching propensity score overlap plots; (2) pre- and post-matching c-statistics and (3) pre- and post-standardized mean differences (SMD) between the two treatment groups.

Patient time under risk and censoring

Patients will be censored in the follow-up period as follows:

Patients will be followed from index date to date of discontinuation of treatment, switch of treatment, death, end of continuous enrollment in the sick fund or end of study period without experiences any event, whichever occurs first.

Sensitivity Analyses

For this study sensitivity analyses are planned according to dosing regimen and patients with prior events of any of the events defined in the combined endpoints.

One separate analysis will be conducted for patients receiving 20mg Rivaroxaban only (standard-dose analysis). Patients will be censored once a different dose was prescribed compared to the index dose of 20mg. For patients receiving initiating 15mg Rivaroxaban baseline characteristics will be outlined descriptively.

Additionally, a separate analysis will be planned where patients with any of the events defined in the combined endpoints within the baseline period 4 quarters prior to index date or “condition after”) will be included in the analyses.

Therefore, sensitivity analyses will result in four separate cohort and patient time datasets for which a propensity score matching and a multivariate analysis will be performed.

Handling of Missing Data

Missing data will not be imputed.

Statistical Software

All analyses will be performed with SAS 9.2.

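### The only date of death described is the start of the quarter; if follow-up is censored on it, stroke and ICH admissions in the quarter of death can be dropped

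*Protocol*

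**What the plan says.** - **Date of death.** Section 9.4, under patient demographics, lists a "date of death, which relates to the beginning of the quarter". No day-level date of death is described. Table 15 lists death only as available.
- **Inpatient data.** The same section says hospital records carry the "date of hospital admission and end of hospital stay" and also "discharge diagnosis code or death in hospital".
- **Censoring.** Section 9.7.1.2, under patient time under risk and censoring: "Patients will be followed from index date to date of discontinuation of treatment, switch of treatment, death", then end of enrolment or of the study period, "whichever occurs first". Between the list and that closing phrase, a short clause refers to patients who have had no event.
- **Follow-up, stated a second time.** Section 9.2.1 ends it at "end of data, disenrollment, discontinuation of index treatment (30 day gap period allowed), occurrence of event or switch of treatment". Death is not in this list.
- **Outcomes.** Section 9.3.3: "Events are defined as hospitalizations with the respective ICD-10-GM diagnosis".
- **Where the rule must stand.** Section 9.7 says its analysis description is sufficient and that no separate SAP will be written. Annex 1 lists no stand-alone documents.

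**The concern.** Two date scales meet in one earliest-date rule. Admissions are known to the day, but death is known only as the first day of its quarter. The recorded death can therefore precede an admission that really came before it, and an earliest-date rule would then end follow-up before the event.

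The events at risk are not a random subset. They are the strokes and haemorrhages that kill quickly, in both the primary effectiveness and the primary safety endpoint. Section 7 gives the ICH analysis as the reason for designating the study a PASS. Section 9.9 acknowledges quarterly resolution only for outpatient diagnoses, so nothing in the protocol would alert a programmer to the problem with deaths.

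**Working it through.** **Step 1: date logic.** Take an ICH admission on 20 February and death on 25 February. The recorded death date is 1 January. The earliest of 1 January (death) and 20 February (event) is 1 January, so on recorded dates the patient is censored event-free. The same holds for any admission after day 1 of the quarter of death. An admission in an earlier quarter precedes the recorded death and is kept.

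**Step 2: index-quarter deaths.** The index date is on or after the first day of its quarter. A death in that quarter is therefore recorded on or before the index date, and follow-up is zero or negative.

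**Step 3: share of fatal events affected.** The protocol gives no lag from admission to death, so this is an assumption. With death uniform over a quarter of Q = 91.25 days and an exponential lag with mean L, the share admitted in the quarter of death is 1 − (L/Q)(1 − exp(−Q/L)):
- L = 3 days: 97%
- L = 7 days: 92%
- L = 14 days: 85%
- L = 30 days: 69%

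**Step 4: share of all events lost.** This is the early fatal share (also an assumption) times the same-quarter share, taken as 0.9:
- ICH, 20%, 30%, 50% fatal: 0.20 × 0.9 = 18%; 0.30 × 0.9 = 27%; 0.50 × 0.9 = 45%
- Ischemic stroke, 5% and 20% fatal: 0.05 × 0.9 = 4.5%; 0.20 × 0.9 = 18%

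**Step 5: power.** Section 9.5 gives about 17,000 Rivaroxaban and 30,000 Phenprocoumon patients and, in the ROCKET-AF row for ICH, rates of 0.005 and 0.007 with power 0.7601. The section states no alpha; two-sided 0.05 is assumed, and rates are treated as proportions.

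Power = Φ[(|p₁ − p₂| − 1.96·SE₀)/SE₁], with SE₀ from the pooled proportion and SE₁ unpooled.
- No loss: p̄ = (85 + 210)/47,000 = 0.00628, SE₀ = 0.000758, SE₁ = 0.000724. (0.002 − 0.001486)/0.000724 = 0.71, power **0.7611**. This reproduces the stated 0.7601 closely.
- 18% lost (295 → 242 events): 0.67
- 27% lost (215 events): 0.62
- 45% lost (162 events): 0.50

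For a 1:1 matched set of 17,000 pairs, the same rates give 17,000 × 0.012 = 204 events. Schoenfeld's formula at HR 0.71 gives power 0.69, and 0.60, 0.55 and 0.44 after the same losses.

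**Step 6: hazard ratio.** To a first approximation, observed HR = true HR × (1 − 0.9·c_R)/(1 − 0.9·c_P), where c is the early fatal share in each arm.
- Equal shares: 0.71 stays 0.71.
- 20% Rivaroxaban, 40% Phenprocoumon: 0.71 × 0.82/0.64 = 0.91.
- 40% Rivaroxaban, 30% Phenprocoumon: 0.71 × 0.64/0.73 = 0.62.

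These pairs show only that bias could go either way. The protocol supports neither.

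**The case against.** The strongest reply is that the protocol does not order this loss.
- The censoring sentence in Section 9.7.1.2 can be read as applying only to patients without an event, so a patient with an ICH admission would not be censored at all.
- Section 9.2.1 ends follow-up at the event and does not list death. Section 9.3.2 says outcome-related hospital stays count as outcome events.
- Section 9.7.1.2 says death; it never names the quarter-start field as the censoring variable. Deaths in hospital could be dated to the day from inpatient records.

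All of this is fair, and it rules out a stronger reading: that the plan as written deletes fatal events and turns ICH into a mainly non-fatal endpoint. It does not close the gap. The no-event clause sits in a sentence that still orders by date, and on recorded dates the patient is event-free at the recorded death. Section 9.2.1 conflicts with Section 9.7.1.2 instead of resolving it. The inpatient death field exists, but no rule uses it.

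A reader might also infer that index-quarter deaths are excluded from the cohort. Section 9.2.2 requires a patient to be observable and insured for at least one day after index and states no test on the death date, so exclusion is possible but not stated. Only the zero or negative follow-up follows directly, and only if the field is used literally.

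**Conclusion.** The point holds in conditional form. The protocol censors at death, describes only a quarter-start date of death, and fixes neither how death is dated nor which date prevails when an outcome admission falls in the quarter of death. Literal use of the field would selectively remove rapidly fatal events from both primary endpoints, understate their rates and reduce power.

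The size rests on assumptions about early fatality and lag that the protocol does not supply. At 20-50% early ICH fatality with 90% in the same quarter, 18-45% of ICH events would be lost and power would fall from 0.76 to about 0.67-0.50. A longer lag makes the loss smaller.

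A reader might infer that the hazard ratio is biased, or biased towards one drug. The documents do not show this: equal proportional loss leaves it unchanged, and no arm-specific fatality is given. Because the protocol says no SAP will follow and the possible loss is selective, this is more than a missing detail and should be settled before analysis.

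**What to change.** In Section 9.7.1.2, state that:
1. A qualifying outcome admission in the quarter of death, while the patient is otherwise still under follow-up, counts as an event and takes precedence over the quarter-start death date.
2. Deaths in hospital are dated by the end of the hospital stay.
3. Other deaths are dated by the insurance end date only if that field is confirmed to be day-level; otherwise by the last day of the quarter of death. The date is never earlier than the patient's last claim. Confirmation is needed because the quarter-start clause in Section 9.4 closes a list that includes insurance begin and end, and may apply to them too.
4. Patients who die in the index quarter stay in the cohort.

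Then align the lists of follow-up ends in Sections 9.2.1 and 9.7.1.2, and add the resolution of the death date to Section 9.9.

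The cost is a few sentences and one derivation rule, using fields that Section 9.4 already describes. The downside is at most one quarter of extra person-time for each out-of-hospital death without an exact date. Choosing quarter end over another fallback is a convention; what matters is that it is fixed in advance and cannot precede an observed event.

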9.5 Study Size

All patients identified in the HRI research database meeting the inclusion criteria will be included in the study. A preliminary feasibility assessment using the HRI database identified a total of approximately 39,600 treatment naïve users of Phenprocoumon and 22,800 treatment

naïve users of Rivaroxaban between Jan 1, 2011 and Sep 30, 2015 for the planned cohort study. However, this preliminary assessment did not consider all of the above listed inclusion and exclusion criteria. We estimate that the actual number of patients might be up to 25% lower.

Rivaroxaban: ~ 17,000 patients

Phenprocoumon: ~ 30,000 patients

Power considerations

Primary effectiveness endpoint – ischemic stroke

Source study	Incidence rate Rivaroxaban	Incidence rate Phenprocoumon	Hazard Ratio	Power
Rocket-AF	0.0134	0.0126	0.94	0.1105
REVISIT-US	0.0054	0.0083	0.65	0.9581
Larsen et al	-	-	0.86	0.2702

Primary safety endpoint – ICH

Source study	Incidence rate Rivaroxaban	Incidence rate Phenprocoumon	Hazard Ratio	Power
Rocket-AF	0.005	0.007	0.71	0.7601
REVISIT	0.0054	0.0096	0.53	1.000
Larsen et al	-	-	0.56	0.9995

9.6 Data management

A completely anonymized file comprising all observations and variables required for the planned analyses will be created from information contained exclusively within the source material. It is required that all analyses will be conducted on the site of the data provider. Data files from the HRI research database must stay in-house due to data protection regulations. Results will be available on an aggregated level.

All statistical processing will be performed using SAS® Enterprise Guide Version 9.2 unless otherwise stated.

It is required that all analyses be conducted on the site of the data provider due to data protection requirements. An independent review of study results will be performed by Xcenda GmbH.

9.7 Data analysis

This section will provide a detailed overview about the statistical methods which will be used in order to answer the research questions. The core statistical elements (analysis populations, definition and measurement of endpoints and other key variables and statistical methodology) are adequately detailed within this section and there will not be a separate SAP.

All analyses will be performed by the Health Risk Institute in coordination with Elsevier Health Analytics and Xcenda GmbH.

9.7.1.1 Demographics and clinical characteristics

In a first step the demographic and clinical characteristics of the patients in both treatment groups will be determined. All variables will be derived in the baseline period.

For continuous variables:

For continuous variables such as age and number of hospitalizations, the mean, median, minimum (min), maximum (max) and the standard deviation (SD) will be reported. The differences between the treatment groups will be estimated by calculating the standardized difference in means (SMD):

$$\frac{\bar{X}_1 - \bar{X}_2}{\sqrt{\frac{(n_1 - 1)S_1^2 + (n_2 - 1)S_2^2}{n_1 + n_2 - 2}}}$$

Phenprocoumon will be used as the reference group.

For categorical variables:

The absolute number and relative proportion of patients with the respective characteristic will be reported. Proportions will be relative to the total sample size of each treatment group. The differences between the treatment groups will be estimated by calculating the standardized difference in means (SMD). Phenprocoumon will be used as the reference group

9.7.1.2 Primary and secondary objectives

The incidence rate and corresponding confidence intervals of the primary and secondary endpoints will be estimated as the number of events per 100 person years (% per year). Cox proportional hazard regression will be used to estimate unadjusted and adjusted hazard ratios (multivariate adjusted as well as 1:1 propensity matched). For all models, hazard ratios (HRs), 95% confidence intervals (CIs) and all other regression coefficients will be reported.

Kaplan-Meier curves will be generated to evaluate the time-to-first event associated with the initial treatment.

Rivaroxaban will be compared to Phenprocoumon. Hence, Phenprocoumon will be the reference category in the analysis. A subset of the variables depicted in Table 2 which were selected on an empirical basis, will be included as covariates in the Cox proportional hazards model.

Propensity Score Matching

In this study, we will additionally use propensity score matching. The propensity score will be calculated as the predicted probability of exposure (i.e. probably of receiving Rivaroxaban), given all that is known about a patient (i.e. patient characteristics and covariates).

The probability itself will be derived from a multivariate logistic regression using the parameters thought to act as confounding variables. The propensity score act as a “balancing score” in that all factors that contribute to the score are expected to be independent between treatment groups if the patient population is matched on propensity score and a stratified table of patient characteristics is examined. That is, after propensity score matching all other factors included in the score are expected to be balanced between the two treatment groups. This will minimize confounding by observed baseline covariates by removing any potential relationship between cofounders and exposure group.

In this study, we will estimate propensity scores from all measured factors noted above. These factors will be entered into a logistic regression model, with the factors as the independent variables (with no further variable selection) and the treatment as the dependent variable. From the resulting model, we will predict probability of treatment for each patient; this probability of treatment will be each patient’s estimated propensity score.

We will perform 1:1 nearest-neighbor matching. After matching, we expect to see balance between the Rivaroxaban and VKA groups with respect to all measured factors. To ensure this, we will examine propensity score balance diagnostics including: (1) pre- and post-matching propensity score overlap plots; (2) pre- and post-matching c-statistics and (3) pre- and post-standardized mean differences (SMD) between the two treatment groups.

Patient time under risk and censoring

Patients will be censored in the follow-up period as follows:

Patients will be followed from index date to date of discontinuation of treatment, switch of treatment, death, end of continuous enrollment in the sick fund or end of study period without experiences any event, whichever occurs first.

Sensitivity Analyses

For this study sensitivity analyses are planned according to dosing regimen and patients with prior events of any of the events defined in the combined endpoints.

One separate analysis will be conducted for patients receiving 20mg Rivaroxaban only (standard-dose analysis). Patients will be censored once a different dose was prescribed compared to the index dose of 20mg. For patients receiving initiating 15mg Rivaroxaban baseline characteristics will be outlined descriptively.

Additionally, a separate analysis will be planned where patients with any of the events defined in the combined endpoints within the baseline period 4 quarters prior to index date or “condition after”) will be included in the analyses.

Therefore, sensitivity analyses will result in four separate cohort and patient time datasets for which a propensity score matching and a multivariate analysis will be performed.

Handling of Missing Data

Missing data will not be imputed.

Statistical Software

All analyses will be performed with SAS 9.2.

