9.2.2 Selection criteria

The study population will consist of all patients, newly initiated on Rivaroxaban or Phenprocoumon with an NVAF diagnosis meeting the following inclusion and exclusion criteria

Inclusion criteria:

- First dispense date of Rivaroxaban (15mg or 20mg - PZN based) or Phenprocoumon (PZN based) between January 1, 2012 and December 31, 2015
- At least two verified outpatient diagnoses or one inpatient diagnosis (main or secondary diagnosis) of NVAF (ICD-10 GM I48.0/ I48.1/I48.2/I48.9) in the individual time frame of 4 quarters before the index date (pre-index period) or within the index quarter
- Patients will be required to have 4 quarters of enrollment for the assessment of baseline characteristics and be observable and insured in the database for at least one day after their individual index date (post-index period)
- ≥ 18 years of age

Exclusion criteria:

- Patients with valvular AF [4 quarters prior to the index date] (see Table 5)
- Pregnancy [4 quarters prior to index date]

- Malignant cancers [4 quarters prior to the index date or “condition after”] (see Table 10)
- Transient cause of AF [4 quarters prior to index date] (see Table 5)
- Patients with VTE (pulmonary embolism or DVT) [60 days before index] (see Table 10)
- Patients with major surgery defined as hip or knee replacement [60 days before index] (see Table 10)
- Prescriptions of OACs (Rivaroxaban, VKA, Dabigatran, Apixaban) before index date [4 quarters prior to index date] (see Table 3, Table 4)
- Patients receiving more than one anticoagulant substance (Apixaban, Dabigatran, Rivaroxaban or Phenprocoumon) or more than one dosage of a substance on the index date (see Table 3, Table 4)
- *For sensitivity analysis* ([see data analysis section](#)) : Patient with any of the events defined in the combined endpoints [4 quarters prior to index date or “condition after”] (see Table 6)
- Patients with dialysis [4 quarters prior to index date] (see Table 10)

[figure not shown]

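### The Cox covariates are an unlisted, empirically selected subset, and neither adjusted analysis accounts for calendar time of initiation

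*Protocol*

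**What the plan says.** Section 9.7.1.2 plans two adjusted analyses for each endpoint.

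- **Multivariable Cox model:** "A subset of the variables depicted in Table 2 which were selected on an empirical basis, will be included as covariates". The subset is not listed, and neither the criterion nor the data behind the selection is given.
- **1:1 matching:** "In this study, we will additionally use propensity score matching". For the score, "we will estimate propensity scores from all measured factors noted above", entered "with no further variable selection".

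For all models, "hazard ratios (HRs), 95% confidence intervals (CIs) and all other regression coefficients will be reported". No allowance for covariate selection is described. Section 9.7 states that the methods are fully set out there and that no separate SAP will be written. Annex 1 lists no stand-alone documents.

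Under section 9.2.2 the first dispensing must fall "between January 1, 2012 and December 31, 2015". The index date is that dispensing date, so it is known for every patient. Neither the baseline list in section 9.3.1 nor any of the 43 rows of Table 2 contains index year, index quarter or another calendar-time term. Section 9.7.1.2 describes no stratification or matching on date, and the Table 30 shell for standardized differences has no row for it.

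**The concern.** There are two separate problems.

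**Selection.** The two adjusted hazard ratios for the same primary endpoint can adjust for different things. If they disagree, the reader cannot tell whether the cause is the method or the covariate list. If the list is chosen on the study data, confounders that look weak but are real may be left out, and an interval computed as though the list had been fixed may not have its nominal coverage. With no list and no SAP, nothing prevents the choice being made after results are seen.

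**Calendar time.** Over four years of starts, the rivaroxaban share of new users may have changed, and so may stroke care, coding and hospital practice. If both the share and the event rate moved, calendar time confounds the comparison. Nothing then stops a phenprocoumon start in 2012 from being matched with a rivaroxaban start in 2015. The planned diagnostics would not reveal this, because they look only at factors that were measured as covariates.

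**Working it through.** The plan gives no figure for either issue, so there is none to reproduce. The section 9.5 table enters only as a benchmark. Its planning hazard ratios are 0.94, 0.65 and 0.86 for ischemic stroke and 0.71, 0.53 and 0.56 for ICH.

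**1. Calendar time.** Inputs from the protocol: starts in 2012–2015, about 17,000 rivaroxaban and 30,000 phenprocoumon patients, hence an overall share of 17,000/47,000 = 36%. Assumptions: equal numbers of starts each year, a share *s* that changes linearly over years *t* = 0 to 3, a background event rate falling by a fraction *d* per year, a true hazard ratio of 1, and no other covariate standing in for calendar time.

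Spurious ratio = [Σ s_t(1−d)^t / Σ s_t] ÷ [Σ (1−s_t)(1−d)^t / Σ (1−s_t)]

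Worked case: shares 0.25, 0.323, 0.397, 0.47 (mean 36%) and *d* = 10%, so relative rates are 1, 0.9, 0.81, 0.729. The rivaroxaban average is 0.837, the phenprocoumon average is 0.873, and the ratio is 0.96.

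| Share 2012 → 2015 | d = 3% | d = 5% | d = 10% |
|---|---|---|---|
| constant 36% | 1.00 | 1.00 | 1.00 |
| 25% → 47% (mean 36%) | 0.99 | 0.98 | 0.96 |
| 10% → 60% (mean 35%) | 0.97 | 0.95 | 0.91 |

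All three share patterns fit the planned sample sizes about equally well, so the overall 36% says nothing about the slope. If event rates rose instead, the bias would run the other way.

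**2. Selection.** An illustrative Poisson simulation used 12 covariates, 12,000 patients, about 335–390 events, a true hazard ratio of 0.86 and 300 runs. Only covariates with p < 0.05 were kept. The rule and the settings are assumptions, since the protocol gives none.

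| Setting | Coverage of 95% CI | Mean HR |
|---|---|---|
| Full model | 0.95–0.97 | 0.85–0.87 |
| Selected, real confounders (log HR 0.1–0.3) | 0.84–0.93 | 0.89–0.94 |
| Selected, covariates unrelated to outcome | 0.95 | – |

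The Monte Carlo error at 0.95 is √(0.95×0.05/300) = 0.013. Coverage falls while the mean shifts, so the loss comes at least partly from residual confounding. The simulation does not isolate an effect on interval width.

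**3. Can the Cox model carry a fixed list?** Assuming one person-year per patient, the first planning row for ICH gives 17,000×0.005 + 30,000×0.007 = 295 events. Suppose nearly all of Table 2 were entered: 43 variables, less cancer and the duplicate severe-liver item, plus 2 for the four-level insurance status, makes 43. Adding 15 terms for 16 separate quarters makes 58, or 295/58 = 5.1 events per parameter. Adding 3 terms for index year makes 46, or 6.4. Pruning the overlapping items improves on both.

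**The case against.** The strongest reply is that the matched analysis already does what is asked. It uses every measured factor without selection, has balance diagnostics, and supplies the outcome table shells (Tables 31–34 are all headed as after matching). A reader might infer that selection undermines both adjusted results. The text does not support that: the selection problem is confined to the Cox model. It is not harmless there, however, because matching is introduced as an addition and neither analysis is named as primary.

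Secondly, the wording is in the past tense and names no data set, so the subset could come from earlier evidence. That is possible, and the coverage concern then falls away. The list is still missing.

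Thirdly, some reduction of Table 2 is sensible. It holds both stroke scores, both comorbidity indices, N18 overall and by stage, and scores beside their components. The protocol itself cites correlation as the reason for the modified index. This stands, and it argues against putting all of Table 2 into the Cox model. It supports a reasoned, named list and gives no support to empirical selection.

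Fourthly, a reader might take one scenario, such as a share rising from 10% to 60% with rates falling 5% per year (ratio 0.95), and say that calendar time accounts for most of the 0.94 planning effect. The documents give neither input, the possible bias starts at zero, and 0.94 is the weakest of six planning effects.

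Finally, because "the type of doctor prescribing (e.g. cardiologist, general practitioner) is included" in the database, as is region of residence, a reader might call their omission an error. Availability alone does not make a variable a necessary confounder, and nothing in the protocol shows that these two are.

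**Conclusion.** The point holds in two limited parts.

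- The Cox adjustment set is unlisted and empirically chosen, with no later document to fix it, and it can differ from the propensity set. Loss of confounder control and under-coverage follow only if selection is made on the study data. In the illustration, coverage was 0.84–0.93 with real confounders and there was no loss without them.
- Calendar time of initiation is absent from both adjusted analyses and from the balance check. The resulting bias ranges from none to about 9%, under the assumptions of equal yearly starts, a linear change in share, event rates falling 3–10% per year and a true hazard ratio of 1. Bias requires both a changing share and a changing event rate. A larger sample would not remove it.

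The upper part of that range would matter against stroke planning effects of 0.94 or 0.86. It matters less against 0.65 or the ICH effects. The change is worth making before analysis because it is nearly free.

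**What to change.** 1. Replace the empirical selection in section 9.7.1.2 with a fixed Cox covariate list, written down in advance and aligned with the propensity set. First remove items that the exclusions leave empty (cancer) and resolve overlaps: for example one stroke score, one comorbidity index, N18 overall or by stage, and only one of the two identical severe-liver code lists.
2. Add index year, or index quarter as a smooth term, to both the propensity and the Cox model, or match within index year. Add it to the Table 30 balance check.

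Cost: index year adds about three parameters (four years less one), matching within year may lose a few pairs, and choosing between overlapping items needs a reasoned decision before analysis. No new data are needed, because the index date is already held for every patient.
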